## 2. SYNOPSIS

Title:	A Retrospective, Observational, Multicentre Study to Collect Clinical Safety and Performance data on POLYMAILLE® C vascular prosthesis
Study Population:	Subjects who did receive POLYMAILLE® C at least one year ago for replacement or bypass of arteries. 2 main sub-populations will be studied depending on location of surgery (abdominal and peripheral), but data will be collected for all subjects who did receive POLYMAILLE® C.
Study Design:	Multi-center retrospective case series
Study Type:	PMCF
Number of subjects:	Data from a minimum of 200 subjects will be evaluated. A minimum of 100 subjects will be evaluated for each main location of surgery (abdominal and peripheral).
Follow-up	At least 1 year follow-up after surgery until a maximum of 5 years.
Study Product:	POLYMAILLE® C vascular prosthesis
Intended use:	POLYMAILLE® C vascular prostheses are indicated for replacement or bypass of arteries presenting aneurysm or obliterative arterial disease. Their indication is restricted to abdominal and peripheral surgery not crossing the knee flexion crease.
Objectives:	Describe safety and performance of POLYMAILLE® C
Performance primary endpoint:	Primary patency rate at 1 year after surgery using POLYMAILLE® C
Safety primary endpoint:	Mortality rate at 30 days after surgery using POLYMAILLE® C
Performance secondary endpoints:	
 
• Procedural success rate
 
• Primary patency rate at 30 days and 6 months after surgery using POLYMAILLE® C
 
• Primary assisted patency rate at 30 days, 6 months and 1 year after surgery using POLYMAILLE® C
 
• Secondary patency rate at 30 days, 6 months and 1 year after surgery using POLYMAILLE® C
 
• Device failure during procedure or at discharge, at 30 days, 6 months and 1 year after surgery using POLYMAILLE® C
 

PROTOCOL	2020-PMC-01
TITLE:	Safety and Performance of POLYMAILLE® C vascular prosthesis
EFFECTIVE DATE:	15 January 2021

Safety secondary endpoints	
 
• Mortality rate during procedure or at discharge, at 6 months and 1 year after surgery using POLYMAILLE® C
 
• Limb salvage rate at 30 days, 6 months and 1 year after surgery using POLYMAILLE® C
 
• Adverse event during procedure or at discharge, at 30 days, 6 months and 1 year after surgery using POLYMAILLE® C
 

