### **5.3. Subjects**

The participating hospitals will screen all potential subjects and will select those who are appropriate for study inclusion, i.e. subjects implanted with POLYMAILLE® C for at least one year, or with complete data to death. As the study explores real world data, there is no exclusion criteria for subjects and all subjects with POLYMAILLE® C implanted for at least one year and up to 5 years will be included in the study.

All data will be retrieved from medical charts for each patient from time of surgery (considered as index date) until a maximum of 5 years after surgery.

Data from a minimum of 200 from 3 to 8 different sites in France will be evaluated. A minimum of 100 subjects will be evaluated for each main location of surgery (peripheral and abdominal).

Not more than 50% of study total enrolled subjects shall pertain to one unique centre.

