## 7.2. Safety endpoints

- Primary safety endpoint is **mortality rate at 30 days** after surgery using POLYMAILLE® C.
- Others study safety endpoints are:
  - **Mortality rate**, *defined as freedom % from death*
  - **Limb salvage rate**, *defined as freedom % from target limb amputation*
  - **Adverse events**, *defined as any documented adverse events, including anticipated (as listed in section 6.2) and non-anticipated adverse events.*

---

PROTOCOL	2020-PMC-01
TITLE:	Safety and Performance of POLYMAILLE® C vascular prosthesis
EFFECTIVE DATE:	15 January 2021

---

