## 8. STATISTICAL CONSIDERATIONS

### 8.1. Statistical design, method and analytical procedures

All the patients participating in the study who met the eligibility criteria will be included in the study population.

A descriptive analysis with clinical characteristics of all patients included in the study will be performed at the index date.

Exploratory analyses will be conducted globally and by the 2 sub-populations. Results will be stratified according to 2 main surgical locations:

- Abdominal surgical location:
  - Aorto-aortic and/or aorto-iliac and/or aorto-femoral repair
- Peripheral surgical location:
  - Peripheral artery repair and extra anatomic bypasses

Since no hypotheses will be tested, study objectives will be addressed using descriptive statistics only. Given the real-world nature of the data, the use of multiple imputation methods for missing data would introduce bias as missing data cannot be considered completely at random (MCAR) or at random (MAR). Variables will not be imputed, with the exception of dates in which the exact day is missing: the missing day will be replaced by the middle day of the month.

Continuous variables will be described with number of patients with valid / missing observations, mean and its 95% confidence interval (95%CI), standard deviation (SD), median, 25 and 75 percentiles (P25 and P75, respectively), minimum and maximum. For non-normally distributed continuous variables geometric mean and its 95%CI will be reported too.

For categorical variables counts and percentages per category will be presented. Missing observations (including invalid observations) will be tabulated as a separate category. If the % of missing data does not exceed 10 %, the calculation of proportions will not include the missing/invalid category in the denominators.

P-values will be presented in the summary tables, in association with the descriptive statistics. In addition, 95% confidence intervals (95%CI) will be presented when considered convenient or relevant. Results will be graphically represented when appropriate to make interpretation easier.

The two-sided level of significance will be set at 0.05 for all the statistical tests performed.

Statistical calculations will be carried out by using R software. More details on the statistical analysis will be provided in the Statistical Analysis Plan.

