### 9.4. Missing data

Some endpoints can be missing for some subjects. Endpoints proportions will be calculated on the number of non-missing observations. No imputation method is planned.

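### The unbounded mid-month rule for a missing day can put a death or graft event on the wrong side of day 30, the cut that defines the primary safety endpoint

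*Protocol*

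**What the plan says.** Section 8.1 (Statistical design, method and analytical procedures) sets a general rule of no imputation, "with the exception of dates in which the exact day is missing: the missing day will be replaced by the middle day of the month". The exception covers every partial date. It gives no lower limit at the operation and no upper limit at the next known date, and it does not treat deaths or events near a time cut differently.

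The synopsis names the primary safety endpoint as "Mortality rate at 30 days after surgery using POLYMAILLE® C", and section 7.2 repeats it. Section 5.3 counts time "from time of surgery (considered as index date"). The section 7 table also places patency, device failure and limb salvage at 30 days. The primary performance endpoint is "Primary patency rate at 1 year after surgery using POLYMAILLE® C".

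Three other places bear on the point:
- Sections 5.3 and 5.3.1 admit a patient with less than one year of follow-up only if the record is complete up to death.
- Section 9.3 plans a consistency check of every variable before the database is frozen, with inconsistencies sent back to sites.
- Section 9.4, on missing endpoints, says "No imputation method is planned".

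**The concern.** A mid-month date can be wrong by up to about two weeks in either direction. That matters little for a five-year outcome, but it is about half of a 30-day window. When a death is known only to its month, and that month contains day 30, the rule decides which side of the cut the death falls on. Nothing about the patient enters that decision.

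At stake is the main safety figure. The strata may hold as few as 100 patients, so a single reassigned death is visible in the reported rate. The same holds for the date of an occlusion or re-intervention used for 30-day patency or device failure.

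A second defect has the same cause: an event in the month of surgery can be dated before the operation. That gives a negative time to event.

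**Working it through.** The protocol states no figure for this point, so there is none to reproduce. The check applies the rule to the calendar.

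**Inputs from the protocol.** Missing day set to mid-month (8.1); time zero is surgery (5.3); cut at 30 days (synopsis, 7.2); at least 100 patients per surgical location and 200 in total (8.2).

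**Assumptions.** The event day is missing and the surgery day is known. The middle day is the 15th, with the 16th as a check. Every surgery date from 2016 to 2019 and every lag within a band has equal weight. All percentages are conditional on a missing day.

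**Formula.** Imputed lag = true lag + (15 − true day of month of the event). The shift runs from +14 (event on the 1st) to −16 (event on the 31st). Therefore:
- A true 30-day event is pushed out only if true lag + 14 ≥ 31, that is, a true lag of 17 to 30 days.
- A later event is pulled in only if true lag − 16 ≤ 30, that is, a true lag of 31 to 46 days.

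**Examples.**

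| Surgery | True death | True lag | Imputed death | Imputed lag | Effect |
|---|---|---|---|---|---|
| 10 March | 5 April | 26 | 15 April | 36 | 30-day death missed |
| 20 March | 25 April | 36 | 15 April | 26 | false 30-day death |
| 20 March | 28 March | 8 | 15 March | −5 | impossible date, still within 30 days |

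**Enumeration.**

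| True lag | Result of the rule | Day 15 | Day 16 |
|---|---|---|---|
| 0-30 | moved past day 30 | 5,040/45,291 = 11.1% | 12.7% |
| 31-61 | moved to day 30 or earlier | 6,106/45,291 = 13.5% | 11.8% |
| 0-30 | dated before surgery | 6,106/45,291 = 13.5% | 11.8% |

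Among true lags of 17-30 days the share pushed out is 5,040/20,454 = 24.6%. Among lags of 0-16 days it is zero (day 15).

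**Why a pre-operative date does not change 30-day status.** It arises only when the event falls in the calendar month of surgery. The longest possible gap within one month is from the 1st to the 31st, which is 30 days. Such an event is always within 30 days, and a negative lag still satisfies a test of 30 days or less.

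**Surgery day missing instead, death date known (day 15).** Of true day 0-30 deaths, 13.5% move past day 30 and 11.1% appear to precede surgery; of day 31-60 deaths, 11.5% move inside.

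**Weight of one death.** 1/100 = 1.0 point; 1/200 = 0.5 point. For example, 2/100 = 2.0% (exact 95% CI 0.2 to 7.0) becomes 3/100 = 3.0% (0.6 to 8.5).

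**One year.** Only 0.9% of events in the first 365 days change side of day 365, so the primary performance endpoint is little affected.

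**The case against.** The strongest objection is that the rule may never be applied to a death that matters. A patient who dies within 30 days can enter only with a complete record up to death, and the sources include electronic health records and claims data. Month-only dates for early deaths may be rare or absent. This stands as a limit on size. It does not close the gap, because the protocol does not define a complete record as one with an exact day of death.

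A second objection is that bounds on partial dates are usual SAP detail, and section 8.1 refers to a SAP that is not shown. That is fair for the bounds, and the SAP may add them. But the protocol does not leave the rule open: it fixes it without condition, and as written it allows the crossing.

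Third, the section 9.3 check could catch a death dated before surgery. It names no check of date order and runs before the freeze, so it would help only if applied after imputation. It cannot detect a plausible date on the wrong side of day 30.

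Three stronger readings are tempting, and the document does not support them:
- A reader might add the 13.5% dated before surgery to the 11.1% pushed out and call about a quarter of 30-day deaths misclassified. Only the 11.1% change status.
- A reader might infer that records with an impossible date will be dropped. Section 8.1 groups invalid with missing observations and leaves both out of denominators when missing data do not exceed 10%, so this could happen. Nothing says that an imputed pre-operative date counts as invalid.
- A reader might see sections 8.1 and 9.4 as contradictory. Section 9.4 concerns missing endpoint values, and section 8.1 states an explicit exception for partial dates. They can be read as a general rule and its exception.

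**Conclusion.** The point holds in limited form. Where the day is missing, the rule in section 8.1 can give a wrong 30-day status: about 11% of true day 0-30 deaths are lost from the window and about 13% of day 31-61 deaths are added to it. These figures assume day 15, evenly spread dates and a missing day of death; day 16 gives about 13% and 12%. The two errors run in opposite directions, so the net effect on the rate cannot be predicted.

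The number of deaths affected is unknown and may be zero. If there is one, the rate moves by 1 point in a stratum of 100 or 0.5 point in 200. Graft events used for 30-day patency and device failure are exposed in the same way. Dates before surgery are a separate data-quality fault: they distort time-to-event values without changing 30-day status. The change is worth making because it is cheap and the endpoint is primary.

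**What to change.** In section 8.1:
1. Bound each imputed event date below by the index date, or by the last date on which the patient was known to be event-free, and above by the next known date.
2. Do not use a mid-month date to classify any 30-day endpoint. Count an event in the calendar month of surgery as within 30 days; no day is needed for that.
3. Where an event is dated only to a month that straddles day 30, query the site through the section 9.3 process.
4. Report 30-day mortality twice if any deaths stay unresolved, once with them counted in and once with them counted out.

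Bounds alone are not enough. They remove the dates before surgery but not the crossing of day 30, which needs items 2 to 4. As an option, add a cross-reference in section 9.4 to the date exception in section 8.1.

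The cost is a few lines of text, a small number of site queries and one extra sensitivity line in the report. No more patients are needed.

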## 5. STUDY DESIGN

POLYMAILLE® C is a retrospective, observational, multicentre, descriptive study which examine short and long-term outcomes of using POLYMAILLE® C. This study will be done on all comers Real World Data to collect clinical safety and performance data on the device.

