### 6.2. Anticipated risks

There is no risk either associated to the study, as there is no procedure performed in the scope of the study. The risks listed below are those related to revascularization surgery and use of grafts and will be the ones monitored.

The type and rate of anticipated risks may differ according to indication and location of the surgical procedure, and may result in:

- Medically important event or reaction
- Persistent or significant incapacity or substantial disruption of the ability to conduct normal life functions
- Re-intervention and re-hospitalization or prolongation of existing hospitalization
- Life-threatening event, reaction up to death.

Early (peri-operative) and late adverse events of abdominal aortic and peripheral arteries open vascular repair with POLYMAILLE® C devices include:

- Bleeding
- Hematoma
- Adherence to surrounding tissues
- Allergic reaction

PROTOCOL	2020-PMC-01
TITLE:	Safety and Performance of POLYMAILLE® C vascular prosthesis
EFFECTIVE DATE:	15 January 2021

- Inflammatory reaction / oedema
- Seroma / lymphorrhea formation
- Wound complications: infection (superficial or deep), revision
- Graft infection
- Graft dilatation
- Pseudo aneurysm / false aneurysm (para-anastomotic aneurysm; non-anastomotic aneurysm)
- Graft stenosis / occlusion
- Limb occlusion
- Amputation (major or minor)
- Secondary aorto-enteric fistula
- Renal dysfunction
- Neurologic deficit
- Pericardial effusion
- Pulmonary complication (pneumonia, perioperative acute pulmonary oedema)
- Cardiac complications (myocardial infarction or arrhythmia, ischemic heart disease, atrial fibrillation)

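### Section 8.1 rules out hypothesis testing, then orders p-values and a 0.05 level without saying what is tested; separately, Sections 8.1 and 9.4 give different denominators for endpoint proportions

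*Protocol*

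**What the plan says.** Section 5 calls this a "retrospective, observational, multicentre, descriptive study", and Section 7 gives its principal objective as describing the device's safety and performance. Section 8.1 follows suit: "Since no hypotheses will be tested, study objectives will be addressed using descriptive statistics only".

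The same section later instructs: "P-values will be presented in the summary tables, in association with the descriptive statistics". It then adds: "The two-sided level of significance will be set at 0.05 for all the statistical tests performed". The nearest thing to a comparison is "Exploratory analyses will be conducted globally and by the 2 sub-populations", followed by a statement that results are stratified by the two surgical locations. Further detail is left to the SAP.

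On denominators, Section 8.1 says of categorical variables: "If the % of missing data does not exceed 10 %, the calculation of proportions will not include the missing/invalid category in the denominators". Section 9.4 bases endpoint proportions on the observed values whatever the amount missing.

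**The concern.** A p-value is the result of testing a hypothesis. A section that excludes hypothesis testing and then requires p-values leaves the analyst to guess which tests are meant, and leaves the reader of the report to guess what each p-value refers to. Section 5.2 says the study is needed to support claims about the device and keep it on the European market, so p-values of unclear meaning could be given more weight than they can bear.

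The only comparison a reader could guess is abdominal versus peripheral. Section 6.2 already warns that "The type and rate of anticipated risks may differ according to indication and location of the surgical procedure". A small p-value between locations would therefore mainly show that the patients and operations differ, and would say little about the device.

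The denominator point is separate and does not depend on p-values. It can change the reported rates themselves, including both primary endpoints.

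**Working it through.** **1. The wording, side by side.** The protocol states no p-value result, power or effect size, so there is no figure to reproduce. Section 8.2 rests the sample size on the realistic number of operated patients.

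- Exclusion of testing (8.1): unqualified, and followed by a restriction to descriptive statistics.
- P-values (8.1): required, with no condition and no test or contrast attached.
- Significance level (8.1): applies to whatever tests are performed. Taken alone it orders none.
- Null value, performance goal, comparator or between-group contrast (Sections 7, 7.1, 7.2, 8.1, 8.2): none stated.
- Surgical location (8.1): a stratum for reporting. No between-stratum test is stated.

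The first two items conflict. The significance-level sentence could stand as a conditional statement, but it has no use if no test is done.

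**2. Scale, on assumptions the protocol does not make.** Cells marked in the Section 7 table up to and including 1 year:

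- Performance: primary patency 3, primary assisted patency 3, secondary patency 3, device failure 4, procedural success 1. Sum 14.
- Safety: mortality 4, limb salvage 3, adverse events 4. Sum 11.
- Total 14 + 11 = 25.

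Assume one abdominal versus peripheral test per cell, each with a true size of 0.05, and no real difference between locations. The expected number below 0.05 is 25 × 0.05 = 1.25. This expectation does not need the tests to be independent. The chance of at least one does: 1 − 0.95^25 = 0.72 under independence. That does not hold here, because the three patency definitions in Section 7.1 overlap and the time points follow the same grafts.

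**3. Denominators (separate point).** Let r be the rate among observed values and m the fraction missing. Section 9.4 reports r. Section 8.1 also reports r when m ≤ 10%. Above 10% it implies that the missing category stays in the denominator, which gives r × (1 − m). With assumed rates and m = 20%:

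- 1-year patency, r = 90%: Section 9.4 gives 90%; Section 8.1 gives 0.90 × 0.80 = 72%.
- 30-day mortality, r = 3%: Section 9.4 gives 3%; Section 8.1 gives 0.03 × 0.80 = 2.4%.

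Above 10% missing, the Section 8.1 rule makes patency look worse and mortality look better than the observed data. At or below 10% the two rules agree.

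**The case against.** The best defence is that the exclusion of hypotheses is tied to the study objectives and means no confirmatory hypothesis. The p-values would then be nominal output of the exploratory analyses, perhaps as one column in a table with abdominal, peripheral and total columns. The SAP could adopt this reading, so a reader who infers that the instructions are impossible to reconcile goes too far. What stands is that the protocol does not say this: the exclusion is unqualified, and the stratification sentence describes separate reporting.

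Other stronger readings are also not supported:

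- That every global estimate needs its own p-value. The text asks for p-values in summary tables and does not say so.
- That the missing null value is itself a defect. Choice of test and contrast can properly be left to the SAP. It matters here only because nothing in the protocol gives the required p-values a meaning.
- That the report faces a 72% risk of a false positive. That needs a test in every cell, independence and equal locations. The protocol states none of these, and Section 6.2 points away from the last.
- That the permissive interval wording ("95% confidence intervals (95%CI) will be presented when considered convenient or relevant") is an error. It is a matter of preference.

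On denominators, one can argue that Section 8.1 covers categorical variables in general and Section 9.4 covers endpoints in particular, so the specific rule governs. That is reasonable, but Section 8.1 does not exempt endpoints, and the endpoint rates are proportions of a categorical variable.

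**Conclusion.** The inconsistency in Section 8.1 is real and is worth correcting in the protocol. Its effect is confined to reporting and interpretation: no success criterion, sample size or data collection depends on a p-value. The contradiction rests on the wording alone. The 1.25 expected chance findings are for scale only and rest on the assumptions stated with them, including equal locations, which the protocol itself gives reason to doubt.

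The denominator conflict is a second, separate defect. It has no effect unless an endpoint has more than 10% missing. The documents do not say how much will be missing: Section 5.3.1 requires one year of follow-up data or complete data to death, but Section 9.2 collects items only as available. If the threshold is passed, the reported rate depends on which section is followed, by 18 percentage points in the assumed patency example (90% − 72%).

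**What to change.** **P-values.** Choose one of two edits to Section 8.1.

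- Delete the p-value sentence and the significance-level sentence. The cost is that nominal p-values are no longer shown.
- If a comparison of abdominal with peripheral surgery is wanted, name it, label it exploratory and unadjusted for multiplicity, and amend the sentence that excludes hypothesis testing to match. The cost is that one comparison must be named in advance. The choice of test can stay with the SAP.

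**Denominators.** State one rule for endpoint proportions and use it in both Section 8.1 and Section 9.4. If the Section 9.4 rule is kept, for example: *Endpoint proportions are calculated among subjects with an observed outcome at that time point, and the number missing is shown beside each rate.* Section 8.1 can then limit its 10% rule to other categorical variables or drop it.

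Both changes are to wording only and need no new data.
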